A Blinded Evaluation of the Effectiveness and Efficacy of the MyHealthyPregnancy Application Statistical Analysis Plan

This study will evaluate the effectiveness and efficacy of the MyHealthyPregnancy App, an app designed to reduce preterm birth risk. This study will use observational cohort data collected at the University of Pittsburgh Medical Center between September of 2019 and February of 2022.

July 18, 2022

[name], [name]

1. Description of the study

MyHealthyPregnancy (MHP) was developed using decision science principles to help prevent preterm birth. An observational cohort trial was conducted at the University of Pittsburgh Medical Center starting in September of 2019 until February 2022. This trial compares the effectiveness of MHP to usual care for pregnant people who delivered at the University of Pittsburgh Medical Center (UPMC). Patients at UPMC were able to download the MHP app after receiving a prescription for the app, as indicated by an EHR variable. Those who were prescribed the app and downloaded it were in the *MHP cohort*. Those who were prescribed the app and did not download it were in the *usual care cohort*. Prescriptions were offered to pregnant people by their care team at an early prenatal visit at UPMC.

EHR data is available for both cohorts of patients. It is the source of all measures, unless otherwise noted.

A linear effects model will be used to evaluate effectiveness by estimating the average treatment effect for the primary endpoint, preventing preterm birth risk.

For each dependent measure, these models will control for primary predictors, as identified in the research literature, that are available in the EHR.

A dose-response model will be used to estimate the effects of continuous measures of non-adherence (as opposed to dichotomous non-adherence, such as not initiating app use). Multiple measures of adherence will be analyzed, including measures of daily use, weekly use, time to initiation, and time from discontinuation to birth.

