1.5. Sample Size Justification

Due to the observational nature of the study and recruitment context, it was not possible to predetermine the sample size based on statistical power for estimating the primary and secondary outcomes. Instead, all participants who met the inclusion criteria between September 2019 and February 2022 were included. The final sample has 12,344 deliveries, divided between the MHP and usual care cohorts (with 7147 in one and 5197 in the other, with their identities currently blinded). This represents about 12,287 different participants (we only have information about the percent of multiple deliveries for participants who downloaded the app, 0.464%). Given the sample sizes in the two cohorts, there is 80% power to detect an effect size of 0.051 days. Assuming that the outcomes are normally distributed with a standard deviation of 10 days (1), the study has 80% power to detect a 0.51 day difference in gestational age at birth between the cohorts.

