2.3. Treatment Usage

At its current stage of development, the MHP app does not prescribe a set dosage, specifying how often patients should interact with it in order to have desired effects. As such, this study investigates app usage as a mediator of the outcome, rather than comparing users who did and did not meet a predetermined dosage.

We will assess the following aspects of usage: how soon after receiving the prescription participants initiated app use (in days); how soon they discontinued app use prior to delivery (in days since initiation); the percentage of days they used it overall (within the usage period); and the percentage of weeks they used it at least once (within the usage period). See Appendix A for details on these use metrics.

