3.1.4. Dose-response analysis

A dose-response analysis will be used to test usage as a mediator of each outcome. Multiple measurements of usage were collected and are listed in Appendix A. Metrics specified in section 2.3 will be created by assessing whether the participant used any app activity on a given day. Logging into the app without activity will not count as app usage because this information was not collected for the full study period. Activity use is also more likely to be associated with engagement with the app than is login alone. Daily usage and weekly usage will be the dependent variables for the dose-response models. As an exploratory analysis, the PCI may be analyzed as a dependent variable. The dose-response relationship will be analyzed for the primary and secondary outcomes using a multiple linear effects model and the confounder adjustment method (12). The model for adherence will be created using 20% of the unblinded data. The dose-response effects for the primary outcome will be reported in the manuscript. The dose-response effect for the secondary outcomes will be reported in the supplemental material.

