EST_GEST_AGE_DAYS	gestational age at the time of birth	Primary outcome
MOM_DELIVERY_WT	weight of mother at time of delivery (kg)	Secondary outcome
PREGANY_DEPRESSION	Diagnosis of depression or active depression at some point during pregnancy (would also be 1 if PREGSTART_DEPRESSION is 1) (binary variable)	Secondary outcome
PREGANY_ANXIETY	Diagnosis of anxiety or active anxiety at some point during pregnancy (would also be 1 if PREGSTART_ANXIETY is 1) (binary variable)	Secondary outcome
PREGANY_PREE	Preeclampsia diagnosed or listed as active problem at any visit while pregnant (binary variable)	Secondary outcome
PNV_COUNT	Number of prenatal appointments attended	Secondary outcome
PNV_TOTSCHED	Number of prenatal appointments scheduled (blank if the same as PNV_COUNT i.e. they didn't cancel any appointments)	Secondary outcome
PREGANY_BEHAVIORALREF	Behavioral health referral at some point during pregnancy (binary variable)	Secondary outcome
PREGANY_SWREF	Social work referral at some point during pregnancy (binary variable)	Secondary outcome
BABY_DISPOSITION	baby's disposition after birth (home health agency, home/self care, children's hospital, cease to breathe, etc)	Exploratory outcome
STILLBORN	whether this baby was stillborn (binary variable)	Exploratory outcome
C_SECTION	Had c-section (binary variable)	Exploratory outcome
BIRTH_WEIGHT	baby's birth weight in grams	Exploratory outcome
NICU_DELIVERYADMISSION	whether the baby was brought to the NICU (binary variable)	Exploratory outcome
ASSUMED_INDUCTION	If a delivery was by c-section prior to 259 days gestation, but there is no documentation of induction then we assume	Exploratory outcome

	it was indicated and this column has a 1 (binary variable). Otherwise, it's 0. Definition came from Hy.	
INDICATED_ONSET	When a delivery form documents that a delivery was induced but not for PROM (binary variable). Definition came from Hy.	Exploratory outcome
CURRENT_PPROM	premature rupture of membranes; diagnosis of O42* during current delivery (binary variable).	Exploratory outcome
VISITNUMBER_F2F	Number of face-to-face visits when pregnant.	Exploratory outcome
PREGANY_PREGINDUCEDHTN_NOPROT	Gestational hypertension without significant proteinuria, could occur during any trimester, childbirth, or puerperium; Diagnosed or listed as active problem at any visit while pregnant. Definition came from EPIC codes	Exploratory outcome

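### The SAP does not settle whether time from last app use to birth is a dose-response exposure; if it is, the exposure contains the primary outcome

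*SAP*

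**What the plan says.** Three places in the SAP bear on this.

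- **Section 1 (Description of the study)** says that a dose-response model will estimate the effects of continuous non-adherence. It then lists the measures to be analysed, "including measures of daily use, weekly use, time to initiation, and time from discontinuation to birth".
- **Section 2.3 (Treatment Usage)** lists four aspects of use. The discontinuation item reads "how soon they discontinued app use prior to delivery (in days since initiation". The daily-use item reads "the percentage of days they used it overall (within the usage period", and the weekly item is built the same way.
- **Section 3.1.4 (Dose-response analysis)** says "Metrics specified in section 2.3 will be created by assessing whether the participant used any app activity on a given day". It then says "Daily usage and weekly usage will be the dependent variables for the dose-response models", with the patient cooperativity index as a possible exploratory addition. On outcomes it says "The dose-response relationship will be analyzed for the primary and secondary outcomes using a multiple linear effects model". The primary-outcome result goes to the manuscript and the secondary-outcome results to the supplement.

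Appendix A gives the primary outcome variable as "gestational age at the time of birth", in days. Preterm birth, the first secondary outcome, is that variable cut at 37 weeks.

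**The concern.** There are two linked problems.

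1. **The sections disagree.** Section 1 counts the gap from last use to birth among the dose-response measures. Section 3.1.4 does not name it for the models, but does not exclude it either, and says that all the section 2.3 metrics will be built. Section 2.3 counts back from delivery and forward from initiation in the same phrase. The first is a gap before birth and the second is a duration of use. An analyst cannot tell whether discontinuation enters a model, or in which form.
2. **One of the possible readings is biased by construction.** A gap that ends at birth gets longer when the pregnancy gets longer. Relating gestational age to it produces an association with no app effect, and any real effect would be mixed with that artefact.

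Section 3.1.4 also calls the usage measures dependent variables although it analyses their relation to the outcomes. This adds to the doubt about what is regressed on what.

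**Working it through.** **Inputs from the SAP (section 1.5).** SD of gestational age at birth: 10 days ("Assuming that the outcomes are normally distributed with a standard deviation of 10 days"). Cohorts: 7147 and 5197; which one is the MHP cohort is blinded, so both sizes are used. Detectable difference: 0.51 day at 80% power. Significance level: 5% (section 3.1), taken as two-sided.

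**The plan's own figure.** (1.960 + 0.842) × 10 × √(1/5197 + 1/7147) = 2.802 × 10 × 0.01823 = 0.511 day. The stated 0.51 day reproduces.

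**The artefact in closed form.** Let G be gestational age at birth (SD 10), D gestational age at last use (SD s), and T = G − D the gap. Assume no app effect and D independent of G. Then:

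- r(T, G) = 10/√(100 + s²)
- slope of G on T = 100/(100 + s²)
- t = r√(n − 2)/√(1 − r²) = (10/s)√(n − 2)

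The SAP gives no distribution of stopping times, so s is an assumption.

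| s (days) | r | r² | slope (day per day) | t, n = 5197 | t, n = 7147 |
|---|---|---|---|---|---|
| 20 | 0.45 | 0.20 | 0.20 | 36.0 | 42.3 |
| 30 | 0.32 | 0.10 | 0.10 | 24.0 | 28.2 |
| 50 | 0.20 | 0.04 | 0.038 | 14.4 | 16.9 |
| 70 | 0.14 | 0.02 | 0.020 | 10.3 | 12.1 |

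**With last use cut off at birth.** The closed form ignores that use cannot continue after delivery. A simulation with no app effect adds this cut-off (300 data sets per setting; G normal with assumed mean 278 and SD 10; assumed initiation at day 70). It covers both readings of section 2.3. Ranges span the two cohort sizes.

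| Assumed stopping pattern | Gap to birth: r | slope | rejected at 5% | Days since initiation: r | rejected at 5% |
|---|---|---|---|---|---|
| Uniform, days 70–280 | 0.16 | 0.026 | 100% | 0.00 | 4–6% |
| Exponential use, mean 60 days | 0.18 | 0.033 | 100% | 0.01 | 7–8% |
| Exponential use, mean 120 days | 0.11 | 0.016 | 100% | 0.03 | 44–58% |
| Exponential use, mean 250 days | 0.08 | 0.010 | 100% | 0.06 | 99–100% |
| Normal, day 250, SD 20 | 0.44 | 0.215 | 100% | 0.06 | 99–100% |

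**Size on the outcome scale.** With uniform stopping, a gap 60 days longer goes with 60 × 0.026 = 1.6 days longer gestation, and 1.6/0.51 is about three times the detectable difference.

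**Direction.** On the gap reading, a longer gap goes with a longer pregnancy, so earlier stopping looks beneficial and the artefact runs against the app. On the days-since-initiation reading, duration of use is capped by birth. Any artefact then links longer use with longer pregnancy. It is small, but detectable when many women use the app until delivery. The two wordings can therefore mislead in opposite directions.

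**The case against.** The strongest reply is that section 3.1.4 is the inferential section and gives a place in the models only to daily and weekly usage, and perhaps the cooperativity index. Section 1 is introductory and fixes no model, and section 2.3 speaks only of assessing use. An analyst working from section 3.1.4 alone would not fit the biased model.

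Much of this stands, and it rules out four readings that a reader might infer:

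- **That the SAP firmly plans this regression and will put it in the manuscript.** The manuscript commitment is in section 3.1.4, which names only daily and weekly usage for the models.
- **That three sections give three definitions of the metric.** Section 3.1.4 omits discontinuation. The conflicting wordings are in sections 1 and 2.3, and the one in 2.3 conflicts with itself.
- **That the outcome would be regressed on itself.** It would be regressed on a quantity that contains it. For s of 30 to 70 days the shared variance is about 10% to 2%.
- **That the false association would be strong.** The large t values reflect the sample size. Correlations of about 0.4 or more need stopping to cluster near term, and the SAP gives no stopping times.

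The reply does not close the point. Section 3.1.4 does not exclude the measure, section 1 expressly includes it, and nothing says which prevails.

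**Conclusion.** The finding is an inconsistency between sections 1, 2.3 and 3.1.4 on whether discontinuation is a dose-response exposure and how it is defined. One of the permitted readings leads to a biased analysis.

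On that reading a significant result is near-certain with no app effect: t is about 10 to 28 for s of 30 to 70 days, and every simulated setting rejected in 100% of data sets. The association itself is weak to moderate and points against the app. Preterm birth is a threshold on the same variable and inherits the problem, although no separate figure was computed for it.

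That the exposure contains the outcome is an identity and needs no assumption. The sizes assume stopping unrelated to birth timing, the stated stopping patterns, no covariate adjustment, and the whole MHP cohort in the model. The main treatment comparison is not affected. The point should be settled before the dose-response models are run.

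**What to change.** 1. **Section 1:** remove the gap from last use to birth from the dose-response measures.
2. **Section 2.3:** define discontinuation once, with a single origin and unit (gestational age at last use is one option). State that it is descriptive only and is not an exposure for gestational age at birth or preterm birth. This should hold for either wording, since duration of use is also capped by birth.
3. **Section 3.1.4:** list the measures that enter the models, in agreement with sections 1 and 2.3, and call them exposures rather than dependent variables.

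These are wording changes with no data cost and no effect on the primary analysis.

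Optional: if the sponsor wants to relate persistence of use to outcome, a landmark analysis would avoid the artefact. It would measure use up to a fixed gestational age among women still pregnant then, and relate it to later outcome. That is an additional analysis and is not needed to resolve this point.

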1.1. Principal research objectives

1.1.1. Primary objective

To compare gestational weeks at birth, for the MyHealthy Pregnancy (MHP) cohort, defined as pregnant people who downloaded the MyHealthyPregnancy app, thereby onboarding into the study, compared to the usual care cohort, defined as pregnant people, who were invited to download the app, but did not do so. Analyses control for predictors of preterm birth.

1.1.2. Secondary objectives

1. To compare *preterm birth*, defined as delivery before 37 gestational weeks, for the MHP and usual care cohorts. Analyses control for predictors of preterm birth.
2. To compare *depression* rates for the MHP and usual care cohorts, using the clinical diagnosis of depression. Analyses control for predictors of depression.
3. To compare *anxiety* rates across MHP and usual care cohorts, using ICD10 codes. Analyses control for predictors of anxiety.
4. To compare rates of *referrals to behavioral health specialists* for the MHP and usual care cohorts. Analyses control for predictors of behavioral health referrals.
5. To compare rates of *referrals to social workers* for the MHP and usual care cohorts. Analyses control for predictors of social work referrals.
6. To compare rates of *preeclampsia* for the MHP and usual care cohorts. Analyses control for predictors of preeclampsia.
7. To compare *sufficient gestational weight gain*¹ for the MHP and usual care cohorts. Analyses control for predictors of gestational weight gain.
8. To compare the number of *prenatal appointments attended* for the MHP and usual care cohorts. Analyses control for predictors of prenatal appointment attendance.
9. To compare the proportion of *required prenatal appointments attended* in the MHP and usual care cohorts. Analyses control for predictors of prenatal appointment attendance.

1.1.3. Exploratory objectives

Exploratory outcomes are ones that might be affected by the app, but lack a known mechanism of action or are of less interest than the primary and secondary outcomes. These outcomes will be reported as supplemental material to the study.

Appendix A contains the full list of each type of measure.

1.2. Study design including blinding

Given the nature of the observational study, patients and providers were not blinded to the treatment condition (MHP, usual care).

The primary statistician will remain blinded to the treatment and usual care cohorts with the exception of using 20% of the unblinded data to evaluate confounders of the outcomes, build a model for propensity score matching, and evaluate confounders of MHP app usage.

1.3. Method of allocation of groups

Participants seeking prenatal care at the UPMC were offered a prescription to download the MyHealthyPregnancy app during an early prenatal visit. Participants were prescribed the app by

¹ Gestational weight gain will be evaluated based on 2009 Institute of Medicine guidelines (11). Recommended gestational weight gain depends on pregravid BMI and if it is a singleton or multiple pregnancy.

their obstetrician or the EHR system and had the option of downloading the app and consenting to trial participation. We have no direct knowledge of how obstetricians decided whether to offer the prescription or if there was encouragement to download the app in addition to the automated EHR prescription. Participants who downloaded the app will be categorized as the MyHealthyPregnancy (MHP) cohort. Participants who did not download the app will be categorized as the usual care cohort.

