3.1.1. Analysis of primary outcomes

The difference in gestational weeks at birth will be evaluated using a linear effects model accounting for confounders of preterm birth, as measured at baseline. We estimate that about 57 out of 12,344 deliveries are for a second pregnancy for participants included in the sample given that 0.464% of participants who downloaded the app had two deliveries in the sample. We have included these women in the sample because we cannot exclude similar women in the usual care cohort given limitations in our data. Likewise, we cannot account for random effects of multiple deliveries using a mixed effects model.

Baseline study variables will be included as confounders in the model if (a) the literature has identified the variable as a confounder of preterm birth risk and (b) they might plausibly have influenced participants' decision to download the app. If, for a variable, the evidence on condition (a) is inconclusive and condition (b) is possible, we will examine the data and include the variable if it passes a 10% change-in-estimates threshold for the outcome or for the likelihood of downloading the app. The change-in-estimate will be calculated by adding each study variable to the model from the literature individually. Only baseline variables will be evaluated as potential confounders, as they could not have been affected by use of the app.

We will report the results of two models for each outcome, one using only confounders identified in the literature and one adding confounders identified empirically (Appendix A). Including fewer confounders will reduce the likelihood that the average treatment effect applies only to an unrepresentative subset of the population. Including additional confounders will reduce the likelihood of statistical bias in estimating the average treatment effect.

The dataset contains many known confounders of preterm birth that could be included in the model including:

- Previous preterm birth (3)
- Race (3)
- Low body-mass index (3,4)
- Insurance type (5)
- Area deprivation index (6)
- Multiple gestations (3)
- Previous spontaneous abortions (7)
- Hypertension (3)
- Diabetes (3)
- Tobacco use (3)

There are also many known predictors of preterm birth that are not in the EHRs, hence not available for this study. They include educational attainment, marital status, interpregnancy interval, relatives who delivered preterm, and genetic predictors of preterm birth (3).

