3.1.2. Analysis of secondary outcomes

Analytical procedures for the secondary outcomes will follow those for the primary outcome. Each outcome will have its own appropriate confounders. As with the primary outcome, these confounders will be based on previous research and specified a priori. As needed, they will be supplemented by empirical analysis of the 20% subset, including baseline covariates specified in Appendix B, with a 10% change-in-estimate threshold for inclusion.

These confounders from the literature are available:

1. Preterm birth defined as delivery before 37 gestational weeks.
 - a. Same confounders as the primary outcome
2. Clinical diagnoses of depression.
 - a. History of anxiety and depression (9)
 - b. Smoking (9)
 - c. Past pregnancy complications or loss (9)

Unavailable: Lack of partner or social support or having a problematic relationship, a history of abuse or child abuse, having had an unplanned or unwanted pregnancy, perceived stress, cognitive style (including “pessimism, anger and rumination; a tendency to be nervous, worried or shy; low self-esteem and low self-efficacy; and high levels of neuroticism or psychoticism”), and single marital status (9).
3. Anxiety rates (using ICD10 codes).
 - a. History of anxiety and depression (9)
 - b. Smoking (9)
 - c. Past pregnancy complications or loss (9)

Unavailable: Same as anxiety (9).
4. Referral to behavioral health
 - a. No confounders identified
5. Referral to social work
 - a. No confounders identified
6. Preeclampsia
 - a. Prior pre-eclampsia (10)
 - b. Chronic hypertension (10)
 - c. Pre-gestational diabetes (10)
 - d. BMI >30 (10)

Unavailable: Antiphospholipid antibody syndrome (10).
7. Sufficient gestational weight gain
 - a. Pre-pregnancy BMI (11)
 - b. Age (11)

Unavailable: Family violence; marital status; food insecurity; maternal pregravid metabolic status; hyperemesis gravidarum; anorexia; past bariatric surgery (11).
8. Number of prenatal appointments attended
 - a. No confounders identified
9. Percent of required prenatal appointments attended
 - a. No confounders identified

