Appendix A

Covariates and Outcomes

Variable Name in EHR	Description	Variable type
PATIENT_ID	ID for each patient not related to patient information	ID
MOM_AGE	Mother's age at time of delivery	Baseline covariate
FINANCIAL_CLASS	Payor at time of delivery from Medipac (insurance level, might be like coverage) (i.e. name like 'UPMC HEALTH NETWORK', 'MED PLUS', 'BEST HEALTH CARE', etc)	Baseline covariate
HOSP_ROLLUP_GROUPING1	Payor at time of delivery from Medipac (insurance type) (i.e. specifies type of UPMC insurance, examples include 'UPMC Commercial', 'Other MA Managed', 'Other Commercial', etc)	Baseline covariate
HOSP_ROLLUP_GROUPING2	Medicare, Medicaid, Self-pay, or Commercial Insurance	Baseline covariate
HPFLAG	Payor at time of delivery from Medipac (UPMC Health Plan Member flag, 1= has UPMC Health Plan, 0=Doesn't have it)	Baseline covariate
PT_ZIP	Patient zipcode	Baseline covariate
AD_ZIP_4	Patient zipcode, location extension (+4)	Baseline covariate
ADI_NATRANK	Area deprivation index, national ranking (0 most deprived, 100 least deprived)	Baseline covariate
RACE	Race, as reported through UPMC	Baseline covariate
MOM_HEIGHT	mother's height at time of delivery (cm)	Baseline covariate
OB_GRAVIDITY	Number of pregnancies (includes current pregnancy, so if it's their first pregnancy, this will be a 1)	Baseline covariate
OB_PARITY	Number of previous deliveries (will be 0 if it's their first pregnancy)	Baseline covariate
OB_FULL_TERM	Number of previous full term pregnancies	Baseline covariate
OB_PREMATURE	Number of previous premature deliveries (prior to 37 gestational weeks)	Baseline covariate
OB_ABORTIONS	Number of previous abortions, including therapeutic/spontaneous abortions	Baseline covariate
OB_LIVING	Number of previous live deliveries	Baseline covariate
OB_SPONTANEOUS_AB	Number of previous miscarriage/spontaneous abortions	Baseline covariate
OB_THERAPEUTIC_AB	Number of previous therapeutic abortions	Baseline covariate
PREGRAVID_WEIGHT	mother's pre-pregnancy weight (kg)	Baseline covariate
GESTAGE_ATVISIT_DAYS	This is the gestational age of the pregnancy at the time of prenatal visit. Calculated using the estimated delivery date ((280-(EPISODE.OB_WRK_EDD_DT-pat_enc.contact_date))).	Baseline covariate
PREGSTART_OBESE	Obese BMI at first prenatal visit (binary variable)	Baseline covariate
PREGSTART_MORBIDOBSE	Morbidly obese BMI at first visit (binary variable)	Baseline covariate

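### Sufficient weight gain and visits attended both accumulate until delivery, so they partly restate the primary outcome, and the baseline-only adjustment rule cannot remove that part

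*SAP*

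**What the plan says.** Section 1.1.2 lists sufficient gestational weight gain (outcome 7), number of prenatal appointments attended (outcome 8) and proportion of required appointments attended (outcome 9).

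- **Outcome 7.** Footnote 1 bases it on the 2009 Institute of Medicine guidelines and adds: "Recommended gestational weight gain depends on pregravid BMI and if it is a singleton or multiple pregnancy". The source field in Appendix A is MOM_DELIVERY_WT, "weight of mother at time of delivery (kg". Section 3.1.2 lists pre-pregnancy BMI and age as confounders.
- **Outcome 8.** Appendix A defines PNV_COUNT as "Number of prenatal appointments attended", with no denominator or time under care. For confounders Section 3.1.2 says "No confounders identified".
- **Adjustment rule.** Section 3.1.1: "Only baseline variables will be evaluated as potential confounders, as they could not have been affected by use of the app". Each outcome gets two models, one with literature confounders only and one adding confounders found by a 10% change-in-estimate rule. Hospital is in all models. Date of first visit is left out of the main models and appears only in a time-effect sensitivity analysis (Section 3.1.5).
- **Fields held.** Appendix A has EST_GEST_AGE_DAYS, "gestational age at the time of birth" (the primary outcome), and GESTAGE_ATVISIT_DAYS, described as "This is the gestational age of the pregnancy at the time of prenatal visit" and classed as a baseline covariate.

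**The concern.** Visits and weight both build up until the day of delivery. A woman who attends and gains exactly on schedule but delivers early has fewer visits and is less likely to be classed as sufficient. A woman who enters care earlier has more visits at the same attendance.

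The cohorts formed themselves by downloading or not (Section 1.3), so differences in gestational length and entry to care are plausible without any app effect. Section 1.4.2 presents these outcomes as measures that app components are meant to affect. A cohort difference in either could then be taken as separate evidence on attendance or weight gain when it only repeats the primary outcome. That holds even if the app truly lengthens gestation: the difference would be a downstream effect, not evidence of changed attendance or weight-gain behaviour.

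**Working it through.** **1. The SAP's own figure (Section 1.5).** With 7147 and 5197 deliveries, √(1/7147 + 1/5197) = 0.01823. Two-sided at 5% and 80% power: (1.960 + 0.842) × 0.01823 = 0.0511 SD, which at SD 10 days is 0.51 day. This reproduces the stated figure. (The 0.051 that the SAP labels as days is in SD units.) The SAP gives no such figure for visits or weight gain, so the inputs below are assumptions shown as ranges.

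**2. Visits, identical attendance in both cohorts.** Assumed: SD 3 to 5 visits, about one visit per week near term, one per four weeks early on. The detectable difference is 0.0511 × 3 = 0.153 to 0.0511 × 5 = 0.255 visits. That equals 1.1–1.8 days of gestation (× 7) or 4–7 days of earlier entry (× 28). Chance of p<α ≈ Φ(d / (SD × 0.01823) − z), with z for α/2:

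| Difference between cohorts | Visits added (d) | α = 0.05 | α = 0.05/9 |
|---|---|---|---|
| Gestation +0.51 day | 0.51/7 = 0.07 | 12–27% | 2–8% |
| Gestation +1 day | 1/7 = 0.14 | 35–74% | 11–44% |
| Gestation +2 days | 2/7 = 0.29 | 88–99.9% | 64–99% |
| Entry 7 days earlier | 7/28 = 0.25 | 78–99.5% | 49–96% |

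A simulation with a common visit schedule rejected at 0.05 in 4% of runs with no difference, 19% at +0.51 day, 54% at +1 day, 97% at +2 days and 94% at 7 days earlier entry. All these figures are without covariates.

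**3. Which models leave the entry effect in.** The literature-only model for outcome 8 has no literature confounder and adds only hospital, so entry is unadjusted there. For the second model, the 10% rule was simulated in a 20% subset of 1234 per cohort (12,344 × 0.20 / 2), with a one-week entry difference, 0.25 visit per week, visit SD 3–4 and entry SD 3–5 weeks (assumed). Gestational age at entry was admitted in 1000 of 1000 runs at every setting. Pregnancy length, being post-baseline, cannot enter either model.

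**4. Weight gain, one woman.** Assumed: mean total gain 14 kg at 40 weeks, SD 5, illustrative lower limit 11.5 kg, late gain r = 0.3 to 0.5 kg per week. P(sufficient) = Φ((14 − r(40 − w) − 11.5)/5) for delivery at w weeks.
- 40 weeks: Φ(0.50) = 69%.
- 37 weeks: Φ(0.20) to Φ(0.32) = 58–63%.
- 34 weeks: Φ(−0.10) to Φ(0.14) = 46–56%.

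**5. Weight gain, between cohorts.** Assumed: 70% sufficient, SD 5 to 7 kg, same r. The proportion becomes Φ(0.524 + r × days/7/SD). At +0.51 day the shift is 0.11–0.25 percentage points; at +2 days it is 0.4–1.0 points, with a 7–22% chance of p<0.05. Simulated rejection was about 6% at +0.51 day and 12% at +2 days, against 5.5% with no difference.

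**6. Would a log-time offset cure outcome 8?** Assumed schedule: every 4 weeks to week 28, every 2 weeks to week 36, then weekly; entry at week 10, delivery at week 39.
- Base rate: 11.5 visits / 29 weeks = 0.3966 per week.
- Two days longer: 11.786/29.286 = 0.4024, up 1.5%, or 0.17 visits. That is 60% of the raw 0.29.
- Entry one week earlier: 11.75/30 = 0.3917, down 1.2%, or −0.14 visits, against +0.25 raw.

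The offset leaves over half of the gestation artefact and reverses the entry artefact.

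**The case against.** The plan has safeguards. Outcome 9 is a proportion, and it need not rise merely because care lasted longer. Gestational age at entry is a listed baseline covariate that the 10% rule would very probably select. Bonferroni-corrected p-values are also reported. These points stand. A reader might infer that early entry goes uncorrected throughout; the documents support that only for the literature-only model. The 78–99.5% figure is therefore an unadjusted one. But outcome 9 does not alter outcome 8, selection by the rule is not guaranteed, and neither touches pregnancy length in outcome 8.

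On weight gain, a reader might infer that the SAP holds every woman to one fixed total whatever her gestation. It does not write out the calculation. It names BMI and plurality as what the target depends on and is silent on gestational age at delivery. If a gestation-specific target was intended, the SAP needs to say so. Nor do the documents support reading the 69% versus 46–56% contrast as a difference between cohorts; step 5 shows the cohort effect is small.

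Finally, a total count is a legitimate total-effect measure, and entering gestational age at birth as a covariate would condition on the primary outcome. Both are right. They argue for a remedy in the definition of the outcome, not in the adjustment set, and they do not make the raw count separate evidence on attendance.

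**Conclusion.** The point holds as a design weakness in two secondary outcomes. As written, both depend mechanically on pregnancy length, and the adjustment rule cannot remove it. Visits carry the quantitative case: a difference detectable at 80% power arises from 1.1–1.8 extra days of gestation or 4–7 days of earlier entry with no change in attendance. At the SAP's own 0.51 day the chance of a significant visit result is modest (12–27%). For weight gain the distortion matters for women who deliver early but is close to nominal error between cohorts at small differences.

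The direction follows from the definitions. The sizes rest on the assumed visit SD and frequency and the assumed weight-gain distribution. The primary analysis is not affected.

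**What to change.** **Outcome 7.** Define sufficiency as gain judged against the amount expected at the woman's own EST_GEST_AGE_DAYS, within BMI and plurality class, and write the calculation out. Keep the total-gain version as supplemental.

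**Outcome 8.** Pre-specify GESTAGE_ATVISIT_DAYS as a covariate in both models. Then either state that the count is interpreted only beside outcome 9, or analyse attended visits over those expected from entry to delivery under the visit schedule actually in use. Do not use a constant-rate log-time offset, because visits become denser near term.

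**Cost.** SAP wording and derived variables from fields already held, set before the full-data models are run and while the analyst is blinded to cohort labels. The expected-visits option also needs the schedule written down. The downside is that results become less directly comparable with reports that use raw totals.
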